### **3.8. Visit Windows**

#### **3.8.1. Treatment Definitions**

Following completion of Screening and Day -1 assessments, eligible hepatic impaired or healthy matched subjects will be enrolled into a cohort and multiple doses of 100 mg BID ENTO (1×100 mg tablet) in the fasted state starting on Day 1 for 5 days.

#### **3.8.2. Definition of Study Day and Predose/Postdose Values**

In analyzing safety data (i.e., AEs, laboratory tests, ECG, and vital signs) in this multiple-dose study, Study Day is the number of days relative to the first dosing day of study drug, calculated as:

$$\left\{ \begin{array}{l} \text{Visit Date} - \text{First Dosing Date of study drug} + 1, \text{ if Visit Date} \geq \text{Dose Date of study drug;} \\ \text{Visit Date} - \text{First Dosing Date of study drug}, \text{ if Visit Date} < \text{Dose Date of study drug.} \end{array} \right.$$

Day 1 is defined as the day of the first dose.

Predose value is defined as the last available off-treatment value collected prior to the first dose of study drug.

Postdose value is defined as any value collected after the first dose of study drug and on or before the date of the last dose plus 30 days.

### **3.8.3. Analysis Windows**

In the safety summary tables, postdose laboratory parameters and vital signs will be summarized as follows:

- Only values obtained at the protocol-specified scheduled time points will be included and summarized. Data collected at unscheduled time points will not be included in the summary tables, but will be included in the listings.
- Data collected on early termination visit will be summarized as a separate visit, labeled as “Early Termination Visit.”
- Data collected on follow-up visit will be summarized as a separate visit, labeled as “Follow-up Visit.”
- Data obtained after the follow-up visit or last dose date plus 30 days (whichever is later) will be excluded from the summaries, but will be included in the listings.

### **3.8.4. Selection of Data in the Event of Multiple Records in a Window**

If multiple, valid, nonmissing numerical observations exist on the same day, records will be chosen based on:

- For predose, the last available record prior to the time of the dose of the study drug will be selected. If there are multiple records with no time recorded on the same day, the average (arithmetic or geometric mean, as appropriate) will be computed for that day.
- For postdose, use the value for the scheduled visit only. If multiple records are available for a scheduled visit, then the average (arithmetic or geometric mean, as appropriate) will be computed for that day.

If multiple, valid, nonmissing categorical observations exist on the same day, records will be chosen based on:

- For predose, select the last available record prior to the time of first dose of the study drug. If there are multiple records with the same time or no time recorded on the same day, the value with the lowest severity will be selected (e.g., normal will be selected over abnormal for safety ECG).
- For postdose visit, the most conservative value within that day will be selected (e.g., abnormal will be selected over normal for safety ECG).

## **4. SUBJECT DISPOSITION AND BASELINE CHARACTERISTICS**

### **4.1. Disposition of Subjects**

A summary of subject enrollment and disposition will be provided by treatment group. This summary will present the number of subjects enrolled, and the number and percentage of subjects in each of the categories listed below. For the “Dosed” category, the denominator for the percentage calculation will be the total number of subjects enrolled for each column. For all other categories, the denominator for the percentage calculation will be the total number of subjects in the Safety Analysis Set for each column.

- Dosed (Safety Analysis Set)
- PK Analysis Set for each analyte
- Completed study drug
- Did not complete study drug with reason for premature discontinuation of study drug
- Completed the study
- Did not complete the study with reason for premature discontinuation of study

In addition, the total number of subjects who were enrolled, and the number of subjects in each of the disposition categories listed above will be displayed in a flowchart.

The following by-subject listings will be provided by subject ID number in ascending order to support the above summary tables:

- Reasons for premature discontinuation of study drug or study

A by-subject listing of subject disposition including cohort, hepatic function group, date of the first/last dose of study drug, study drug completion status, reason for study drug discontinuation, study completion status, reason for study discontinuation, and PK set status (indicating whether or not a subject is included in a PK analysis set) will be provided by subject ID number in ascending order.

### **4.2. Baseline Characteristics**

#### **4.2.1. Demographics and Baseline Characteristics**

Subject demographic data (age, sex, race, and ethnicity), baseline characteristics (CPT score, body weight, height, and BMI), and estimated glomerular filtration rate (eGFR) by Cockcroft-Gault (CG) method will be summarized using descriptive statistics for the safety analysis set. Eight summary statistics (sample size, mean, standard deviation, median, Q1, Q3, minimum, and

maximum) will be presented for continuous data (age, weight, height, BMI, and eGFR). Age (in years) will be calculated from the date of first study drug dosing if dosed, enrollment if not dosed. The number and percentage will be presented for categorical data (sex, race, ethnicity, and CPT Score). Additionally, body weight, height and BMI will be summarized for males and females separately. Note that the summary of demographics and baseline characteristics will be provided by hepatic function group and smoking status within cohort.

In addition to the summary tables, a listing will be provided for all demographics and baseline characteristics data.

#### **4.2.2. Medical History**

Medical history data will be listed only by subject including cohort, hepatic function group, condition or procedure reported term, onset date, ongoing status, and resolution date (if applicable).

Medical history data will not be coded.

#### **4.3. Study Drug and Meal Administration**

A listing will be provided to display study drug administration data, including cohort, hepatic function group, study drug dosing date and time, and fasting status.

#### **4.4. Protocol Deviations**

A by-subject listing will be provided for those subjects who violated at least 1 inclusion or exclusion criterion, regardless of whether they were exempted or not by the sponsor. The listing will present the entry criterion (or criteria if more than 1 violation) that subjects did not meet and related comments, if collected.

Protocol deviations occurring after subjects entered the study are documented during routine monitoring. Any deviations identified will be evaluated to determine if it justifies excluding the subject from any analysis sets.

## 5. ANALYSIS OF PHARMACOKINETIC DATA

PK parameters will be computed for all subjects in the PK analysis set. The analyte(s) presented in [Table 5-1](#) will be evaluated if data are available.

**Table 5-1. Study Treatments and Associated Analytes**

Cohort	Treatment	Analyte
1	ENTO 1 × 100 mg BID	ENTO and/or its metabolites (if applicable)
2	ENTO 1 × 100 mg BID	ENTO and/or its metabolites (if applicable)
3	ENTO 1 × 100 mg BID	ENTO and/or its metabolites (if applicable)

The analytes and parameters presented in [Table 5-2](#) will be used to evaluate the objectives of the study.

**Table 5-2. Primary and Secondary PK Parameters for Each Analyte**

Analyte	Parameters	
	Primary	Secondary
ENTO	AUC tau , C tau , and C max	T max , C last , T last , λ z , T 1/2 , CL/F, and V z /F, and as appropriate, AUC 0-12 (Day 1), AUC inf (Day 1), AUC%exp (Day 1)

### 5.1. Estimation of Pharmacokinetic Parameters

PK parameters will be estimated using WinNonlin® software by application of non-compartmental methods. The linear log trapezoidal rule will be used in conjunction with the appropriate non-compartmental model (usually input Model 200 for oral dosing), with input values for dose, time of dose, plasma concentration, and corresponding real time values, based on drug dosing times whenever possible.

Samples BLQ of the bioanalytical assays that occur prior to the achievement of the first quantifiable concentration will be assigned a concentration value of zero to prevent overestimation of the initial AUC. Samples that are BLQ at all other time points will be treated as missing data. The nominal time point for a key event or dosing interval ( $\tau$ ) may be used to allow for direct calculation of the AUC over specific time intervals. The appropriateness of this approach will be assessed by the PK Scientist on a profile-by-profile basis.

Accurate estimation of several PK parameters, such as λz and T1/2, are dependent on an accurate estimation of the terminal elimination phase of drug. The appropriateness of calculating these parameters will be evaluated upon inspection of PK data on a profile-by-profile basis by the PK Scientist.

A list of individual data on determination of plasma half-life and corresponding correlation coefficient will be provided including intensive PK sampling day, number of data points in regression, start time, end time, and correlation coefficient.

## 5.2. Statistical Analysis Methods

PK parameters will be summarized for individual subjects in the PK analysis set (see Section 3.2.3) and summary statistics will be provided for each analyte (when possible) evaluated in the study by hepatic function group and smoking status within cohort.

### 5.2.1. General Considerations for Statistical Analyses

Nine descriptive statistics (sample size, mean, standard deviation, coefficient of variation [%CV], minimum, median, maximum, Q1, Q3) will be presented for PK concentration data. For concentration values BLQ, the number of subjects with values of BLQ will be presented.

For PK parameter data, the geometric mean, geometric mean 95% CI, and the mean and standard deviation of the natural-log transformed values will be presented in addition to the summaries mentioned above.

The following tables will be provided for each analyte/hepatic function group within cohort:

- Individual subject concentration data and summary statistics
- Individual subject PK parameters and summary statistics

The following figures will be provided for analytes by hepatic function group within cohort:

- Individual subject concentration vs. time—linear and semi-log scale
- Mean ( $\pm$  SD) concentration vs. time—linear and semi-log scale
- Median (Q1, Q3) concentration vs. time—linear and semi-log scale

The following listings will be provided:

- PK sampling details by subject, including differences in scheduled and actual draw times, procedures, and sample ages
- Individual data on determination of plasma half-life and corresponding correlation coefficient

### 5.2.2. Statistical Comparative Analysis

To evaluate the PK effect of hepatic impairment on ENTO and/or its metabolites (if applicable), the PK parameters ( $AUC_{0-12}$  (day 1),  $AUC_{tau}$  (day 5), and  $C_{max}$  (day 1 and 5)), will be compared between impaired hepatic function group (test) vs normal hepatic function group (reference)

within each smoking status group (Cohort 1 only) after natural log transformation. The primary comparison will be based on day 5 PK parameters ( $AUC_{\tau}$  and  $C_{\max}$ ).

To evaluate the smoking effect on PK of ENTO and/or its metabolites (if applicable), the PK parameters ( $AUC_{0-12}$  (day 1),  $AUC_{\tau}$  (day 5), and  $C_{\max}$  (day 1 and 5)), will be compared between smoking group (test) vs nonsmoking group (reference) within Cohort 1 hepatic impaired subjects after natural log transformation. The primary comparison will be based on day 5 PK parameters ( $AUC_{\tau}$  and  $C_{\max}$ ).

A parametric (normal theory) ANOVA model will be fitted to the natural log-transformed PK parameter using SAS® PROC MIXED. The model will include hepatic function as a fixed effect. The 2-sided 90% CIs will be constructed for the ratio of geometric least-squares means (impaired hepatic function group /normal hepatic function group).

The following SAS® PROC MIXED code will be used in the comparison analysis described above and the 90% confidence intervals (CIs) will be constructed for the ratio of geometric least-squares means of PK parameters.

```
Proc Mixed method=reml;
*where smoking status eq "Yes"; Cohort 1 only
*where smoking status eq "No"; Cohort 1 only
*where hepatic impaired, Cohort 1 only
  class hepgrp;
  *class smoking status;
  model lnest = hepgrp / ddfm=kr;
  repeated / group = hepgrp;
  lsmeans hepgrp / e diff cl alpha = 0.1;
  estimate 'Impaired versus Normal' hepgrp 1 -1 / cl alpha = 0.10;
  *model lnest = smoking status / ddfm=kr;
  *repeated / group = smoking status;
  *lsmeans smoking_status / e diff cl alpha = 0.1;
  *estimate 'Smoking vs Nonsmoking HI subjects in Cohort 1' smoking_status 1 -1 / cl
alpha = 0.10;
  ods output Estimates = LS_Diffs LSMeans = LS_Means CovParms = MSE;
Run;
```

The ESTIMATE statement will be used to produce the point estimate and 90% CI on natural-log scale for the differences between hepatic function groups/smoking groups. The test/reference comparison ratio and associated 90% CI will be calculated by exponentiation of the natural-log scale point estimate and the corresponding lower and upper limits.

Ninety percent CIs for the GLSM ratio of the test and reference groups will be calculated for each ENTO and/or its metabolites (if applicable) PK parameter in each cohort, consistent with the 2 one-sided t-tests approach {[U.S. Department of Health and Human Services Food and Drug Administration Center for Drug Evaluation and Research \(CDER\) 2001](#), U.S. Department of

Health and Human Services Food and Drug Administration Center for Drug Evaluation and Research (CDER) 2003}. For the comparison between hepatic function groups: if the upper bound of the 2-sided 90% CI of the GLSM ratio for  $AUC_{\tau}$  and  $C_{\max}$  (Day 5) is smaller than 2.0, we will reject the hypothesis that subjects with moderate (or mild or severe as applicable) hepatic impairment exhibit average PK parameter (ie,  $AUC_{\tau}$  and  $C_{\max}$  [Day 5]) increases of at least 100% for analyte ENTO and/or its metabolites (if applicable) compared with subjects with normal liver function.

The PK parameters  $T_{1/2}$ ,  $CL/F$  and  $V_z/F$  will be compared between hepatic function groups (for Cohort 1: the comparison between hepatic function groups will be by smoking status groups) using a nonparametric method of Wilcoxon rank sum test. The following SAS® PROC NPAR1WAY code will be used for such nonparametric comparison.

```
proc npar1way wilcoxon;  
  class hepgrp;  
  var aval;  
run;
```

To evaluate the protein binding of ENTO and/or its metabolites, the percent of unbound ENTO and/or its metabolites at  $T_{\max}$  and another later time point will be summarized by hepatic function group and smoking status group (Cohort 1 only). Protein binding data for individual subject will be presented in a listing.

For subjects hepatic impairment, the relationship between plasma PK exposure parameters  $AUC_{\tau}$  and  $C_{\max}$  and overall CPT impairment score will be explored using Spearman correlation analysis and examined graphically. The relationship between the PK parameters ( $AUC_{\tau}$  and  $C_{\max}$  on Day 5) and baseline lab tests (albumin, total bilirubin, prothrombin time, and International Normalized Ratio [INR]) will be also explored using Spearman correlation analysis and examined graphically for hepatic impaired subjects and for all subjects by hepatic function group.

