4.3.3. Healthy Matched Controlled Subjects

Healthy matched controlled subjects meeting *any* of the following additional exclusion criteria are not to be enrolled in this study:

- 1) Serious or active medical or psychiatric illness that, in the opinion of the Investigator, would interfere with subject treatment, assessment, or compliance with the protocol. This would include renal, cardiac, hematological, hepatic, pulmonary (including chronic asthma), endocrine (eg, diabetes), central nervous, gastrointestinal (including an ulcer), vascular, metabolic (thyroid disorders, adrenal disease), immunodeficiency disorders, active infection, or malignancy that are clinically significant or requiring treatment.
- 2) History of liver disease.

- 3) Have taken any prescription medications or over-the-counter medications, including herbal products, within 28 days prior to start of study drug dosing, with the exception of vitamins and/or acetaminophen and/or ibuprofen
- 4) Positive test for drugs of abuse, including alcohol at Screening or on Day -1/check-in
- 5) Subjects will be required to refrain from the use of nicotine, nicotine-containing products (including cigarette smoking) or THC-containing products for at least 14 days prior to first dose of study drug, and during the course of the study through the follow-up visit

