5.6.2. Other Protocol Restrictions

- Subjects will be required to refrain from the consumption of food and beverages containing alcohol products 72 hours prior to the first dose of study drug and during the course of the study through the follow-up visit.
- Subjects will be required to refrain from the use of nicotine or nicotine-containing products and THC-containing products for at least 14 days prior to first dose of study drug, and during the course of the study through the follow-up visit. This restriction does not apply to smoking hepatic impairment subjects enrolled in Cohort 1.
- Subjects will be required to refrain from consumption of grapefruit juice, grapefruits, and Seville orange juice 72 hours prior to the first dose of study drug and during the course of the study through the follow-up visit.
- While confined at the study center, tea, coffee, chocolate, and other foods and beverages containing caffeine and other methyl xanthines will be prohibited on each dosing day. At all other times, caffeine-containing beverages and foodstuffs may be served or withheld in accordance with normal study center practice. Caffeine-containing beverages and foodstuffs will not be restricted while subjects are outside of the clinic.

- Subjects will be encouraged to avoid strenuous or prolonged exercise, as well as saunas, steambaths, and sunbathing or other prolonged UV exposure, eg, in a tanning salon, from the Screening evaluation until completion of the follow-up visit, as these activities are known to affect certain clinical laboratory test parameters, (eg, creatine kinase (CPK)) and will provide false indicators of a potentially treatment-related toxicity.

Upon every admission to the clinic, each subject will be questioned as to their compliance with the above protocol restrictions. If a subject is unable to comply with any of the restrictions described above, the subject's continued participation in the study will be reevaluated by the Investigator in consultation with the Sponsor.

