### **Cohort 1 (Moderate Hepatic Impairment) Initial Cohort**

Up to 40 subjects: 20 with moderate hepatic impairment (10 smokers [at least 8 evaluable] and 10 non-smokers [at least 8 evaluable]), 20 matched healthy controls (at least 8 evaluable healthy controls matched to smokers with moderate impairment, and at least 8 evaluable healthy controls matched to non-smokers with moderate hepatic impairment).

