**Figure 1-2. Study Schema – All Cohorts**

#### **1.4. Sample Size and Power**

Eight evaluable subjects per hepatic function group (for Cohort 1, it is 8 evaluable subjects per hepatic function group within each smoking status group) will provide  $\geq 89\%$  probability for the 90% confidence interval (CI) for the geometric least-squares mean (GLSM) ratio of PK parameters (AUC or  $C_{\max}$ ) for ENTO in the hepatic impairment/dysfunction group(s) versus the appropriate group of matched, healthy controls, to be within limits of 50% to 200%. The calculation assumes an expected ratio of geometric least-squares means of 1.0 in PK parameters and inter-subject standard deviation of 0.455 for the natural logarithm-transformed pharmacokinetic parameters for ENTO. The assumption is based on the data obtained from a prior clinical study of ENTO (Study GS-US-339-0111).

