#### **3.3. Strata and Covariates**

Each subject in the control group will be matched to a subject with impaired hepatic function by age ( $\pm 10$  years: age  $\geq 18$ ), sex, and body mass index ( $\pm 20\%$ :  $18 \leq \text{BMI} \leq 40$ ).

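### The Cohort 1 smoker-stratum ratio is read as the effect of hepatic impairment and put through the 2.0 rule, although its healthy controls must all be non-smokers

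*SAP*

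**What the plan says.** SAP 5.2.2 sets out to evaluate the effect of hepatic impairment by comparing the impaired group (test) with the normal group (reference) "within each smoking status group (Cohort 1 only) after natural log transformation". Hepatic function is the only term in that model. Protocol 8.6 also stratifies the Cohort 1 comparison by smoking status.

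The decision rule in SAP 5.2.2 covers the comparison between hepatic function groups. If the upper 90% limits for Day 5 AUCtau and Cmax are below 2.0, "we will reject the hypothesis that subjects with moderate (or mild or severe as applicable) hepatic impairment exhibit average PK parameter" increases of at least 100%. The rule does not exempt the smoker stratum, and its conclusion is worded for the impairment class, not for a stratum. For the Wilcoxon tests of T1/2, CL/F and Vz/F in Cohort 1, "the comparison between hepatic function groups will be by smoking status groups".

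On the controls:

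- Protocol 4.3.3, item 5: "Subjects will be required to refrain from the use of nicotine, nicotine-containing products (including cigarette smoking) or THC-containing products for at least 14 days" before the first dose, and then through follow-up.
- Protocol 5.6.2 repeats the nicotine and THC restriction and gives one exemption: "This restriction does not apply to smoking hepatic impairment subjects enrolled in Cohort 1".
- SAP 3.3: "Each subject in the control group will be matched to a subject with impaired hepatic function by age", sex and BMI. Smoking is not a matching factor.
- The SAP's Cohort 1 description plans "at least 8 evaluable healthy controls matched to smokers with moderate impairment", and SAP 1.4 counts "8 evaluable subjects per hepatic function group within each smoking status group".

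Impaired smokers, by contrast, must smoke at least 10 cigarettes a day and plan to continue during the study (Protocol 4.2.2, item 7).

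**The concern.** In the smoker stratum, smoking differs completely between the two arms: all impaired subjects smoke and no eligible control does. Stratifying cannot remove a factor that coincides with the group being compared, and the model has no smoking term. The stratum estimates impairment and smoking together, but it is labelled as impairment alone.

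The protocol itself treats smoking as a possible confounder. Section 1.3 reports lower exposure in Cohort 1 smokers, points to CYP1A2 induction, and restricts Cohorts 2 and 3 to non-smoking impaired subjects for that reason. The Cohort 1 analysis does not carry this reasoning through. If smoking lowers exposure, the smoker-stratum ratio is too low as a measure of impairment, and the 2.0 rule can declare a doubling excluded when it is not. Section 1.3 says the data will inform dosing recommendations in liver dysfunction, so a wrong conclusion here bears on the primary objective.

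The SAP also does not say what smoking-status value a healthy control carries. If the template WHERE line for smokers were applied to each subject's own status, no control would remain and the contrast could not be estimated.

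**Working it through.** **Inputs.** From SAP 1.4: 8 evaluable subjects per group and SD 0.455 on the log scale. From SAP 5.2.2: a two-sided 90% interval and the 2.0 threshold. From SAP 1.3: 10 enrolled per group. Assumed, because the documents give none: a smoking exposure ratio *s* of 0.9, 0.8 or 0.7 in impaired subjects.

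**The plan's own figure.** SE = 0.455 × √(2/8) = 0.2275, with 14 df and t(0.95) = 1.761. At a true ratio of 1.0 the noncentrality is ln 2 / 0.2275 = 3.05, and the chance that the upper limit is below 2.0 is 89.4%. This recovers the stated figure of at least 89% as an upper-limit probability, which is the event the 2.0 rule uses. For the event as worded in SAP 1.4, both limits within 50% to 200%, I get 78.9%. That mismatch is a separate matter and does not affect this point.

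**What the smoker stratum estimates.** Expected ratio = impairment ratio × *s*. With a true impairment ratio of 2.0 and *s* = 0.7, it is 2.0 × 0.7 = 1.4.

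**When the rule passes.** At the planned SD the half-width is 1.761 × 0.2275 = 0.4007, a factor of 1.493. The upper limit is below 2.0 when the observed ratio is below 2.0 / 1.493 = 1.34.

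**False-pass rate at a true impairment ratio of 2.0.** P = P(T₁₄(δ) > 1.761), with noncentral T and δ = (ln 2 − ln(2*s*)) / 0.2275 = −ln(*s*) / 0.2275.

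| *s* | Expected ratio | δ | 8 per group | 10 per group |
|---|---|---|---|---|
| 1.0 | 2.0 | 0 | 5.0% | 5.0% |
| 0.9 | 1.8 | 0.463 | 11.4% | 12.6% |
| 0.8 | 1.6 | 0.981 | 23.9% | 27.8% |
| 0.7 | 1.4 | 1.568 | 43.9% | 51.7% |

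The SAP code fits a separate variance per group. Simulating that model with Satterthwaite df at 8 per group gives about 5%, 11%, 23–24% and 43%.

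**If AUCtau and Cmax must both pass** (pooled variance, same ratio for both, assumed between-parameter correlation 0.5 to 0.9, simulation):

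| *s* | Correlation 0.5 | 0.7 | 0.9 |
|---|---|---|---|
| 1.0 | 1.2% | 1.9% | 3.2% |
| 0.9 | 3.8% | 5.3% | 7.8% |
| 0.8 | 10.9% | 13.8% | 18.0% |
| 0.7 | 27.0% | 30.9% | 36.6% |

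**Away from the boundary.** At a true impairment ratio of 2.5 the per-parameter rates for *s* = 0.9, 0.8 and 0.7 are 1.6%, 5.0% and 13.9%, against 0.5% with no smoking effect.

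**Protocol 8.6 criterion (interval within 50% to 200%).** At a true ratio of 2.0 the rates are nearly the same: 11.4%, 23.8% and 43.5%. If impairment has no effect at all (ratio 1.0), smoking pushes the interval out at the lower end: the chance of lying within the limits falls from 78.9% to 74.6%, 61.1% and 40.3%.

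**The case against.** The strongest reply is that the plan already holds the clean answer. The non-smoker stratum is an uncontaminated impairment contrast of the same size, and smokers are compared with non-smokers among impaired subjects. Since all controls follow one non-smoking rule, the smoker-stratum ratio should be about the non-smoker ratio times the smoking ratio, so a careful reader can separate the two. That is true, but the SAP does not tell the reader to do so. It applies the rule to each stratum under the impairment label and does not say which stratum governs.

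A second reply is that the table reads one stratum alone. If a claim needed both strata to pass, the false-claim rate per parameter at a true ratio of 2.0 would be 0.05 × 0.114 = 0.6%, 0.05 × 0.239 = 1.2% and 0.05 × 0.439 = 2.2% (strata independent). If either sufficed, it would be 1 − 0.95 × 0.886 = 16%, 1 − 0.95 × 0.761 = 28% and 1 − 0.95 × 0.561 = 47%, of which 1 − 0.95² = 10% arises without any smoking effect. This stands as a qualification: the plan states no combination rule, so the effect on an overall claim is undetermined.

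Three more points are fair. A true ratio of exactly 2.0 is the least favourable case. The smoking ratios are assumed, and Protocol 1.3 lists CYP1A2 among the lesser pathways. The WHERE lines are commented template code, and SAP 1.3 and 1.4 imply that controls are assigned by match, so the empty stratum is a gap in specification and not a forecast.

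Finally, the Cohort 3 trigger uses non-smokers only, and the Wilcoxon tests carry no decision rule. These points limit the consequence. They do not make the smoker-stratum ratio an estimate of impairment.

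**Conclusion.** The concern holds. With controls assigned by match, the smoker-stratum contrast in SAP 5.2.2 estimates impairment and smoking combined. Neither document labels it so, and a pre-stated rule draws a conclusion about impairment from it. The direction of bias follows from the protocol's report of lower exposure in smokers, if smoking is the cause. Its size is not known: the 11%, 24% and 44% are per parameter, for that stratum read alone, at a true impairment ratio of 2.0 and assumed smoking ratios of 0.9, 0.8 and 0.7. They are lower when both parameters must pass or when the true ratio is above 2.0, and there is no bias if smoking has no effect. The smoker-stratum Wilcoxon comparisons mix the two effects in the same way. The non-smoker stratum, the smoking comparison within impaired subjects and the Cohort 3 trigger are not affected. Because the error touches the primary objective and a stated decision rule, it needs correcting before the SAP is finalised.

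**What to change.** In SAP 5.2.2, with matching wording in Protocol 8.6:

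1. Base the Cohort 1 estimate of the impairment effect, the 2.0 rule and the 50% to 200% check only on impaired non-smokers versus their healthy matched controls.
2. Report impaired smokers versus their matched non-smoking controls, including the Wilcoxon comparisons, as the combined effect of impairment and smoking, outside both criteria.
3. Replace the smoking-status WHERE lines with explicit group definitions that state how each control is assigned, for example by the smoking status of the impaired subject it was matched to.

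The cost is wording and code. No subjects or samples are added and the matched design is unchanged. What is given up is any impairment-only claim from the smoker stratum.
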